### 1.5. Summary of Nonclinical Pharmacokinetics

Following intravenous (IV) or SC administration (1 mg/kg) in Sprague-Dawley rats, the apparent plasma terminal elimination half-life (t1/2) of CPT31 was 3.2 and 5.5 hours, respectively, and SC bioavailability was 53%. Similarly, following IV or SC administration (1 or 3 mg/kg, respectively) in cynomolgus macaques, the t1/2 of CPT31 was 7 and 18.6 hours, respectively, and SC bioavailability was 78%. CPT31 given IV to Sprague-Dawley rats or monkeys has a low volume of distribution (134 mL/kg and 96 mL/kg, respectively), suggesting that it is largely confined to the plasma compartment. Plasma protein binding studies revealed that 5  $\mu$ M CPT31 is  $\geq$ 96% bound in rat, minipig, dog, monkey, and human plasma.

Both Cmax and AUC of CPT31 upon SC administration to Sprague-Dawley rats are linear (but not fully dose proportional) at increasing dose levels up to 40 mg/kg. Terminal half-life is consistently between 4 and 8 hours at dose levels ranging from 3-75 mg/kg.

A distribution/excretion study using radioactive [I]-CPT31 suggested that CPT31 is eliminated via renal clearance, as expected for a mid-molecular weight compound (average 9,029 Daltons). Composed of D-peptides, CPT31 is not expected to enter peptide catabolic pathways.

Non-parametric superposition of available cynomolgus macaques PK data (Table 1) and allometric scaling to humans predicts that a 0.03 mg/kg SC injection every third day would give a trough level  $\sim$ 13-22 nM (117-199 ng/mL). Therefore, this dose is tentatively set as the expected human therapeutic dose in order to achieve a trough CPT31 level of  $\geq$ 4  $\times$  the

serum-adjusted IC90 against diverse strains in human PBMCs (~16 nM), as described above. However, the PK profile in humans remains to be established, and the estimated effective dosing will change accordingly.

**Table 1: Pharmacokinetic Parameters of CPT31 in Cynomolgus Macaques**

Day	Dose (mg/kg/day)	Sex	AUC 0-24 (hr*ng/mL)	C max (ng/mL)
1	5	M	252 000	15 100
		F	248 000	16 100
	10	M	356 000	23 000
		F	393 000	25 700
	20	M	686 000	41 600
		F	627 000	37 800
	14	M	264 000	16 700
		F	270 000	17 500
	10	M	369 000	25 500
		F	391 000	25 200
	20	M	396 000	30 800
		F	676 000	54 500

Abbreviations: AUC0-24 = area under the plasma concentration-time curve from time zero to 24 hours postdose; Cmax = maximum observed plasma concentration; hr = hour; Tmax = time of the maximum observed plasma concentration.

There is little potential for significant CPT31 drug-drug interactions involving cytochrome P450 based on direct inhibition studies in liver microsomes. There is also low intrinsic clearance of CPT31 in microsomes as well as low to medium CPT31 intrinsic clearance in hepatocytes. In all species tested (rat, minipig, dog, monkey, and human), clearance rates are greater in hepatocytes than in liver microsomes, indicating the possibility of a non-cytochrome P450-mediated mechanism of biotransformation. Furthermore, CPT31 did not significantly inhibit key cell transporters (P-glycoprotein, Breast Cancer Resistance Protein, organic anion transporting polypeptide ([OATP]1B1, OATP1B3, organic cation transporter [OCT]2, OAT1, OAT3, multidrug and toxin extrusion [MATE]1, MATE2-K), indicating low therapeutic potential for drug-drug interactions as a result of transporter inhibition.

Putative metabolites formed during non-NADPH-dependent CPT31 clearance observed in rat, monkey, and human microsomes were sought and not detected in a study using liver microsomes. By contrast, another study sought putative CPT31 metabolites formed during clearance in rat, monkey, and human hepatocytes. While partial degradation in all species was observed, no specific species attributable to CPT31 metabolism were detected.

## 1.6. Study Rationale

This is the first time CPT31 will be administered to humans. The principal aim of this study is to obtain safety and tolerability data when CPT31 is administered SC as a single dose to healthy subjects. This information, together with the PK data, will help establish the doses and dosing regimen suitable for future studies in patients.

## **1.7. Benefit-risk Assessment**

Subjects in this study will not gain any clinical benefits. Study subjects and others may benefit in the future from information learned from this study. Specifically, information learned in this study may lead to the development of safe and effective interventions to treat and/or prevent HIV transmission.

The risks of participation are primarily those associated with adverse reactions to the investigational medicinal product (IMP), although there may also be some discomfort from collection of blood samples and other study procedures.

Phlebotomy may lead to discomfort, feelings of dizziness or faintness, and/or bruising, swelling and/or infection. Good venipuncture practices reduce the pain and likelihood of bruising and secondary infection. Precautions will be taken with subjects who have a history of fainting or other vasovagal events during blood draws, including having the subject lie down during the procedure.

Subcutaneous injections can cause injection site swelling, warmth, and discomfort. These ISRs generally resolve within 3 days. Inadvertent administration of study product into a vein or into a nerve can occur. Injections are only administered by trained designated study personnel, and numerous precautions are taken to minimize this risk.

Electrocardiograms (ECGs) have no major risks. However, mild pain may be associated with removal of the electrodes and mild skin irritation may develop at the sites of electrode attachment.

## **2. OBJECTIVES AND ENDPOINTS**

### **2.1. Objectives**

The primary objective of the study is:

- to assess the safety and tolerability of a single SC dose of CPT31 in healthy subjects

The secondary objectives of the study are:

- to characterize the single SC dose PK of CPT31
- to identify and characterize antibodies to CPT31

### **2.2. Endpoints**

#### **2.2.1. Primary Endpoints**

The primary safety endpoints for this study are as follows:

- incidence and severity of adverse events (AEs)
- incidence of laboratory abnormalities, based on hematology, clinical chemistry, and urinalysis test results

- 12-lead electrocardiogram (ECG) parameters
- vital signs measurements
- physical examinations
- anti-CPT31 antibodies, e.g., immunoglobulin (Ig)G, IgM

### **2.2.2. Secondary Endpoints**

The single ascending dose PK outcome endpoints of CPT31 are as follows:

- AUC from time zero to infinity ( $AUC_{0-\infty}$ )
- AUC from time zero to the time of the last quantifiable concentration ( $AUC_{0-t_{last}}$ )
- $C_{max}$
- time of the maximum observed plasma concentration ( $T_{max}$ )
- $t_{1/2}$
- apparent total plasma clearance (CL/F)
- apparent volume of distribution ( $V_z/F$ )
- renal clearance ( $CL_R$ )
- amount of drug excreted in the urine ( $A_e$ )
- percentage of dose excreted unchanged in the urine ( $F_e$ )

Other PK parameters may also be reported.

## **3. INVESTIGATIONAL PLAN**

This will be a single SC dose study.

### **3.1. Overall Study Design and Plan**

This study will comprise a placebo-controlled, double-blind, single-dose, sequential-group design. Overall, it is planned for 32 healthy subjects to be studied in 4 groups (Groups A1 to A4), with each group consisting of 8 subjects. In each group, 6 subjects will be randomized to receive SC CPT31 and 2 subjects will be randomized to receive matching placebo.

Potential subjects will be screened to assess their eligibility to enter the study within 28 days prior to the first dose administration.

Each subject will participate in 1 treatment period only. Subjects will reside at the Clinical Research Unit (CRU) from Day -1 (the day before dosing) to Day 6. All subjects will return for a Follow-up visit 28 to 30 days after dosing.

Based on the ongoing review of the safety, tolerability, and PK results, additional nonresidential visits may be required. The number of additional visits per subject will not exceed 3 and will not extend beyond 30 days after dose administration.

[figure not shown]
All groups will be divided into 2 cohorts, with each cohort being dosed 72 hours apart. The first (sentinel) cohort will comprise 2 subjects, with 1 subject receiving CPT31 and 1 subject receiving placebo. The second cohort will comprise 6 subjects, with 5 subjects receiving CPT31 and 1 subject receiving placebo.

The maximum total duration of study participation for each subject (from Screening through Follow-up visit) is anticipated to be approximately 8 weeks.

Dose escalation will occur a minimum of 7 days after all subjects complete all Day 6 assessments in the previous dose group.

[figure not shown]
An overview of the study design is shown in [Figure 1](#) and the planned dose levels in are shown in [Figure 2](#). A Schedule of Assessments is presented in [Appendix 6](#).

**Figure 1: Study Schematic**

Abbreviations: CRU = Clinical Research Unit, N = number of subjects.

**Figure 2: Planned Dose Levels**

Abbreviations: N = number of subjects; SC = subcutaneous.

### **3.2. Study Start and End of Study Definitions**

The start of the study is defined as the date the first enrolled subject signs an Informed Consent Form (ICF). The point of enrollment occurs at the time of subject number allocation. The end of the study is defined as the date of the last subject's last assessment (scheduled or unscheduled).

### **3.3. Additional Groups**

Following review of the safety, tolerability, and PK data, additional dose groups may be added to the study. Up to 3 further groups of 8 subjects (6 active:2 placebo) may be included.

The requirement for additional groups will be decided by the Protocol Safety Review Team (PSRT), comprised of the Investigator, Sponsor Representative, Medical Monitor, and NIH Division of AIDS (DAIDS) Medical Monitor. Changes will be documented in the Trial Master File (TMF), and the IRB will be notified.

### **3.4. Discussion of Study Design, Including the Choice of Control Groups**

A sequential-group, ascending-dose design has been chosen for safety reasons as CPT31 is in the early stages of clinical development, with this study being the first time it will be administered to humans. Subcutaneous doses have been chosen for the study, as this is the intended clinical route of administration.

Continuous 12-lead ECG monitoring will be included for Groups A3 and A4 in order to allow assessment of the relationship between CPT31 concentrations and QT interval

corrected for heart rate (QTc), with a view to supporting a potential thorough QT study waiver.

Based upon the nonclinical data, the planned duration of the study is considered adequate to achieve the study objectives.

This study will be double-blind and placebo-controlled in order to avoid bias in the collection and evaluation of data during its conduct. Placebo has been chosen as the control treatment to assess whether any observed effects are treatment-related or simply reflect the study conditions.

Conducting the study in healthy subjects mitigates the potential confounding effects of the disease state and concomitant medications.

### 3.4.1. Dose Interval

Dosing at each dose level will be such that 2 subjects (1 CPT31 and 1 placebo) will be dosed 72 hours before the remaining 6 subjects. After dosing the first 2 subjects on a separate day, a minimum of a 5-minute dosing interval for the remaining 6 subjects in each dose-ascending cohort is considered acceptable. Continuation to dose the remaining 6 subjects will be made by the PSRT.

### 3.5. Selection of Doses in the Study

Based on activity in human PBMCs infected with diverse primary isolates, the estimated effective serum trough concentration of CPT31 is 16 nM (145 ng/mL) (4x the serum-adjusted IC90 in PBMCs).

Human PK modeling predicts that a dose of 0.03 mg/kg administered every third day will be optimal to maintain CPT31 serum trough levels in a narrow range (~13-22 nM, 117-199 ng/mL) that is close to the target trough concentration of 16 nM while minimizing total exposure (Cmax ~50 nM, 452 ng/mL) over the course of an envisioned future short-duration (~2-week) multiple ascending dose human study. We propose a starting dose of 0.01 mg/kg in this first-in-human single ascending dose study, with subsequent dose escalations to 0.04 mg/kg (4-fold increase), 0.12 mg/kg (3-fold increase), and 0.24 mg/kg (2-fold increase). The safety margins for the 0.01 mg/kg human dose relative to rat and monkey NOAELs are 97 and 320, respectively (Table 2).

**Table 2: Human Safety Margin Estimates for CPT31**

Study Type	Species	Duration	NOAEL		HED (mg/kg)*	Human Safety Margins**
			mg/kg	mg/m 		
Safety Pharmacology						
CNS	Rat	Single dose	60	360	9.7	970
CNS	Monkey	14 days	20	240	6.5	650
Respiratory	Rat	Single dose	60	360	9.7	970
Respiratory	Monkey	14 days	20	240	6.5	650
Cardiovascular	Monkey	14 days	20	240	6.5	650

General Toxicology						
Repeat-dose	Rat	14 days	ND	ND	ND	ND
	Rat	28 days	6	36	0.97	97
	Monkey	14 days	10	120	3.2	320

CNS = central nervous system; HED = human equivalent dose; ND = not determined; NOAEL = no observed adverse effect level.

\* Based on allometric conversion between species based on mg/kg dose levels. Allometric conversion factors used for rat and monkey were 6.2 and 3.1, respectively. Assumes body weights for rat, monkey, and human of 0.15, 3, and 60 kg, respectively.

\*\* Calculated by dividing the HED by the proposed CPT31 clinical start dose of 0.01 mg/kg.

The planned IMP dose levels for the study are shown in Table 3.

**Table 3: Planned Investigational Medicinal Product Dose Levels**

Group	Subject Numbers	Dose
A1	0101 – 0108	0.01 mg/kg or placebo
A2	0109 – 0116	0.04 mg/kg or placebo
A3	0117 – 0124	0.12 mg/kg or placebo
A4	0125 – 0132	0.24mg/kg or placebo

Dose levels should not increase by more than 5-fold for predicted nonpharmacologically active dose levels and by more than 3-fold for predicted pharmacologically active dose levels ( $\geq 0.03$  mg/kg by SC injection every third day).

The highest dose level may exceed the top dose shown in the above table, provided the dose escalation stopping rules are not exceeded ([Section 3.7](#)).

Details of all doses administered in the study will be documented in the TMF.

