### 3.6. Dose Escalation

Doses will be administered in an escalating manner following satisfactory review by the PSRT of the safety, tolerability, and PK data (up to 5 days postdose) from the lower dose levels. Any clinically significant results will be discussed before dose escalation continues. Interim PK data will also be reviewed in terms of dose escalation and to confirm that the study design remains appropriate. Doses may be reduced and may be lower than the starting dose. There will be a minimum of 7 days between completion of Day 6 assessments in the previous dose group and dosing in the next dose group to allow sufficient time for an adequate safety review.

Dose escalation will only occur if data from all participants in the dosing group have been reviewed by the PSRT.

An interim safety report, summarizing results from all available safety assessments, will be sent to the Sponsor prior to the start of each successive group.

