### **3.7. Dose Escalation Stopping Rules**

Following discussion among the PSRT, dose escalation will stop if:

- Clinically relevant signs or symptoms of similar nature occur in 2 or more subjects in a group that, in the opinion of the Investigator, warrant stopping of dose escalation.
- One or more subjects experience a serious AE (SAE) that is considered to be related to IMP.
- Two or more subjects experience a Grade 3 or 4 AE or laboratory abnormality that is considered to be at least possibly related to IMP.
- There is evidence of clinically significant increases in liver function tests (aspartate aminotransferase, alanine aminotransferase, alkaline phosphatase, bilirubin, and/or gamma-glutamyl transferase), defined as 3 times the upper limit of normal in 3 or more subjects in a group (confirmed with repeat testing).
- Clinically significant increases in serum creatinine or blood urea nitrogen, defined as 1.5 times and 2 times the upper limit of normal, respectively (confirmed with repeat testing), in 3 or more subjects in a group.

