**MODIFICATIONS TO PROTOCOL:**

**General Revisions:**

Section 3.5: Wording revised as no systemic exposure specifically defined in section 3.7

Section 5.2: Correction/clarification of timings

Section 5.4: Updates to appearance of CPT31 and placebo solution information and potential for required study blinding actions/processes.

**ADDITIONAL RISK TO THE SUBJECT:** There are no additional risks to the subjects.

---

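### Optional doses above 0.24 mg/kg have no pre-stated dose or exposure limit, and the PSRT's review of interim PK has no criterion

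*Protocol*

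**What the plan says.** Four parts of the protocol bear on this.

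- **Section 3.5, after Table 3.** The planned top dose is 0.24 mg/kg (Group A4), but "The highest dose level may exceed the top dose shown in the above table, provided the dose escalation stopping rules are not exceeded". The condition refers to Section 3.7. Doses should not rise "by more than 3-fold for predicted pharmacologically active dose levels".
- **Section 3.3.** "Up to 3 further groups of 8 subjects (6 active:2 placebo) may be included". The PSRT decides, and "Changes will be documented in the Trial Master File (TMF), and the IRB will be notified".
- **Section 3.6.** Escalation needs a satisfactory PSRT review of safety, tolerability and PK from all participants in the group. It adds: "Interim PK data will also be reviewed in terms of dose escalation and to confirm that the study design remains appropriate". No value or action is attached.
- **Section 3.7.** "Following discussion among the PSRT, dose escalation will stop if" one of five things occurs: similar clinically relevant symptoms in two or more subjects of a group; one related SAE; at least possibly related Grade 3 or 4 events or laboratory abnormalities in two or more subjects; liver tests at 3 times the upper limit of normal in three or more subjects of a group; or creatinine at 1.5 times or urea nitrogen at 2 times that limit in three or more subjects of a group.

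The overall stopping rules in Section 3.8 and the SAP add no dose or exposure limit. The only margins given for general toxicity are at the starting dose: "The safety margins for the 0.01 mg/kg human dose relative to rat and monkey NOAELs are 97 and 320, respectively".

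**The concern.** Section 3.5 points to Section 3.7 as the condition for going above 0.24 mg/kg, but every rule there needs an effect to have appeared first. Nothing in it looks ahead to the exposure the next group will receive. The one forward-looking step, the PK review, is left to judgement.

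This matters most for the optional groups, because they would have the smallest margins. Section 1.4 identifies the kidney as a target organ in both species: renal tubular degeneration accounted for most of the deaths and moribund sacrifices in the 14-day rat study, and tubular degeneration and necrosis were major findings in the 14-day monkey study. Section 1.7 says subjects gain no clinical benefit, so the limit should be set before the data arrive. The optional groups also follow the lighter approval route: a PSRT decision, a file record and IRB notification. Under Appendix 5, a protocol amendment needs IRB and Division of AIDS approval.

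**Working it through.** **1. The plan's own margins.** Inputs from Table 2: NOAELs of 6 mg/kg (rat, 28 days) and 10 mg/kg (monkey, 14 days); conversion factors 6.2 and 3.1. HED = NOAEL / factor; margin = HED / human dose.

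- Rat: 6/6.2 = 0.968; 0.968/0.01 = 96.8 (stated 97).
- Monkey: 10/3.1 = 3.23; 3.23/0.01 = 323 (stated 320, from the HED rounded to 3.2).

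Both reproduce.

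**2. What the remaining limits allow.** Three added groups at 3-fold steps give 0.24 x 3 = 0.72, then 2.16, then 6.48 mg/kg. Using the rounded HEDs (0.97 and 3.2):

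| Dose (mg/kg) | Rat margin | Monkey margin | Volume, 70 kg at 15 mg/mL |
|---|---|---|---|
| 0.24 | 4.0 | 13.3 | 1.12 mL |
| 0.72 | 1.35 | 4.4 | 3.4 mL |
| 2.16 | 0.45 | 1.5 | 10.1 mL |
| 6.48 | 0.15 | 0.49 | 30.2 mL |

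**3. Exposure implied by the stated prediction.** Section 3.5 predicts, for 0.03 mg/kg every third day, Cmax of about 50 nM and troughs of about 13-22 nM; 1 nM = 9.029 ng/mL. Assume one compartment and, first, no absorption delay. Then k = ln(50/trough)/72, a single dose contributes C0 = (50 - trough) x 9.029, and AUC0-24 = C0 x (1 - exp(-24k))/k.

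- Trough 13: k = 0.01871 per hour, C0 = 334 ng/mL, AUC0-24 = 6,459 hr*ng/mL.
- Trough 22: k = 0.01140 per hour, C0 = 253 ng/mL, AUC0-24 = 5,308 hr*ng/mL.

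With first-order absorption (ka assumed 0.1-0.5 per hour) the range is 5,688-7,305. Overall: AUC0-24 of 5,308-7,305 and single-dose Cmax of 253-379 ng/mL at 0.03 mg/kg.

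**4. Scaling to higher doses.** Two cases are shown. The first is dose-proportional: x8 for 0.24 mg/kg and x24 for 0.72 mg/kg. The second uses the log-log slope of the Day 1 AUC values in Table 1 (5, 10 and 20 mg/kg), which is 0.696, taken as 0.70: 24^0.70 = 9.25.

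| Case | AUC0-24 (hr*ng/mL) | Margin to rat 92,300 | Margin to monkey 380,000 | Cmax (ng/mL) |
|---|---|---|---|---|
| 0.24, proportional | 42,000-58,000 | 1.6-2.2 | 6.5-8.9 | 2,020-3,030 |
| 0.72, proportional | 127,000-175,000 | 0.53-0.72 | 2.2-3.0 | 6,070-9,100 |
| 0.72, slope 0.70 | 49,000-68,000 | 1.4-1.9 | 5.6-7.7 | 2,300-3,500 |

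The NOAEL Cmax values are 6,900 ng/mL (rat) and 25,400 ng/mL (monkey).

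**5. Break-even.** The slope at which 0.72 mg/kg just reaches the rat AUC is ln(92,300 / AUC0-24 at 0.03 mg/kg) / ln 24. It is 0.84 for 6,459 and 0.90 for 5,308, and about 0.80-0.88 with absorption. The rat value is therefore passed only if human PK is closer to proportional than a slope of roughly 0.80-0.90.

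**The case against.** The strongest reply is that Section 3.7 is not the only gate. Section 3.6 requires a satisfactory PSRT review, including PK, before any escalation, and the PSRT includes the Division of AIDS Medical Monitor. Sentinel subjects are dosed 72 hours ahead, chemistry is checked daily on Days 2-6, and the sponsor, FDA or IRB may stop the study at any time. Section 3.3 does not say that added groups must go upward, and three 3-fold steps are the extreme reading: 30 mL at 6.48 mg/kg is hardly practical as an injection, although no maximum volume is stated. All of this stands and lowers the urgency. It does not supply a criterion, and 3.4 mL at 0.72 mg/kg is not clearly ruled out, since Section 5.2 allows more than one syringe.

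The toxicology is also milder than a short summary suggests. In the 28-day rat study the renal findings were classed as non-adverse and recovered. In the 14-day study, 63 of 64 rats at 10 and 20 mg/kg/day tolerated the drug; the one sacrificed moribund had a plasma level about 3-fold above its group peers. The NOAELs come from repeat dosing, and the single-dose maximum tolerated doses were far higher (100 mg/kg rat, 40 mg/kg monkey).

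Three stronger readings are tempting but unsupported:

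- **That the planned doses are unsafe, or that 0.72 mg/kg would pass the rat NOAEL exposure.** Group A4 stays below it in the proportional case, 0.72 mg/kg is not a planned dose, and its exposure falls on either side depending on the slope. It stays below the monkey value in both cases.
- **That total AUC after one human dose can be set against 92,300.** That figure is one day's AUC in rats dosed daily for 28 days, so the comparison is mismatched.
- **That Appendix 7's line "Section 3.5: Wording revised as no systemic exposure specifically defined in section 3.7" proves the gap.** It describes a change to superseded wording. The current text of Sections 3.3, 3.5, 3.6 and 3.7 is enough.

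**Conclusion.** The point holds as a gap in the rules for optional doses, and closing it would be a cheap improvement. High confidence applies only to the text: the permission to exceed 0.24 mg/kg is tied to rules with no dose or exposure limit, the PK review has no threshold, and the step and group caps allow doses above both NOAEL equivalents.

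The mg/kg margins follow directly from Table 2. The exposure figures are less certain. They rest on the protocol's approximate prediction for a different regimen, a one-compartment model, assumed absorption rates, and a choice between proportional scaling and a slope taken from monkeys at 5-20 mg/kg. These assumptions cannot settle which side of the rat value 0.72 mg/kg would fall on. Observed human PK can, and the trial collects it before each escalation without saying how it would be used. Passing a repeat-dose NOAEL exposure once would mean lost margin, not evidence of harm.

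**What to change.** 1. **Section 3.7:** add that dose escalation stops, unless the protocol is amended, if Cmax or AUC0-24 projected from observed human PK to the next dose exceeds the rat NOAEL values (6,900 ng/mL; 92,300 hr*ng/mL). State the projection method, for example a power model fitted to all doses so far. Apply the review to the highest observed individual as well as the group mean, because a mean can hide one subject with high exposure.
2. **Section 3.5:** make the permission to exceed 0.24 mg/kg subject to that rule.

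On the stated prediction, Group A4 would proceed. A 0.72 mg/kg group would proceed if human PK is as sub-proportional as Table 1, and would need an amendment if PK is near proportional.

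The cost is one rule and one clause. No new samples are needed: ten postdose PK samples through 24 hours and a PK review before each escalation are already planned. The blind can be kept, because placebo samples are not analyzed and a group mean and an unlabelled maximum can be reported to the PSRT. The downside is less freedom to add doses above 0.24 mg/kg without an amendment.
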